4.2 Treatment Administration

Alisertib will be administered orally BID on days 1-7 of each cycle; one cycle is defined as 21 days (days 8-21 will be rest days). Patients will be instructed to take each oral dose of alisertib with 8 ounces (1 cup, 240 mL) of water, with or without food. Doses on the same day should be taken approximately 12 hours apart (but *at least* 6 hours apart). All tablets are to be ingested whole; patients who have difficulty swallowing tablets will be excluded from the study. Antiemetic agents may be administered at the discretion of the investigator. Neutralizing antacids and calcium-containing supplements cannot be taken from 2 hours prior to alisertib dosing until up to 2 hours after dosing.

Patients will be dispensed the appropriate number of tablets required for each cycle. Treatment compliance will be assessed based on return of unused alisertib tablets and completion of a study medication diary; patients will be asked to bring completed diaries and pill bottles to each visit, and compliance will be reviewed by the study team each cycle. For MF patients only, from Cycle 1-6, on Day 1 of each cycle, when the patient comes in for clinic visit, they will be given study drug supply for one cycle (1 cycle=21 days). Beyond Cycle 6, if the patient's condition is stable, then they will be required to come in on Day 1 of every odd cycle (every 6 weeks) for study visit. In that case, patients will be given study drug supply for 2 cycles.

If a dose is missed due to patient error/oversight, they will be instructed to take the dose within 6 hours of the normal time. If more than 6 hours have elapsed, that missed dose should be omitted, and the patient should resume treatment at the next scheduled dosing time point. All missed/omitted doses and the reason will be reported on the diary. If a dose is vomited, it should not be re-taken. If a dose is held due to toxicity or investigator's discretion, the patient should be instructed to resume treatment at the investigator's discretion, taking into account all of the dose modification/discontinuation guidelines provided below.

From Cycle 1-6, in order for each new cycle of therapy to begin, MF patients must meet the following criteria: (if the cytopenias in AMKL patients are considered-disease related/due to AMKL then the following neutrophil and platelet count requirements do not apply. If cytopenias are considered due to the study drug, then the counts must be

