- ANC must be $\geq 1000/\text{mm}^3$
- Platelet count must be $\geq 50,000/\text{mm}^3$
- In addition, all toxicities considered to be related to therapy with alisertib must have resolved to \leq Grade 1 or the patient's baseline values

For MF patients only, from Cycle 1-6 patients will be required to come in for study visit at beginning of every cycle (every 3 weeks). Beyond Cycle 6, if the patient's condition is stable, then they will be required to come in on Day 1 of every odd cycle (every 6 weeks) for study visit. In that case, for those visits when an MF patient is not coming to clinic for study visit, CBC and CMP will be done in an outside laboratory convenient for the patient, and results will have to be faxed to the clinic.

Patients can start their treatment at home only after the treating physician has reviewed the laboratory results and determined that they are able to continue treatment. For these cycles, the study coordinator will contact the patient on/prior to Day 1 to inform them if they can or cannot start the new cycle, and also check compliance regarding study drug intake.

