4.3 Dose Modifications & Delays

Any patient who receives at least one dose of study therapy will be evaluable for toxicity endpoints. Each patient will be assessed for the development of toxicity according to the timeframe referenced in Section 5). Toxicity will be evaluated according to the NCI's CTCAE v 4. To manage excessive toxicity, reduction of the total alisertib dose can be done by reducing the daily dose administered and/or by interruption of the schedule treatment within a cycle.

In general treatment delays of up to 1 week for any reason are permitted. If a patient fails to meet the above-cited criteria for a new cycle of therapy, then initiation of the next cycle *should be delayed* for up to 1 week. At the end of that week, the patient should be re-evaluated to determine whether the criteria for retreatment have been met. Should treatment need to be delayed for more than 1 week because of incomplete recovery from treatment-related toxicity, the dose of alisertib will be reduced (see table below) to 40 mg BID when therapy resumes. A second dose reduction to 30 mg BID may occur should treatment need to be delayed for more than 1 week because of incomplete recovery from treatment-related toxicity at the 40 mg BID dose. Patients who require further dose reduction will be removed from the study. Should treatment need to be delayed for more than 2 weeks at any dose, therapy with alisertib will be discontinued.

Dose Level	Alisertib¹
Level 1 (starting dose)	50 mg
Level -1	40 mg
Level -2	30 mg
Level -3	Discontinue

¹ Doses are administered orally, BID on days 1-7 of each cycle.

4.3.1 **Dose Modifications for Hematological Toxicities**

If a patient experiences any of the following hematological toxicities during the dosing period, dosing will be discontinued for the remainder of that cycle and the dose will be decreased by 1 level (-10 mg) for all subsequent cycles of treatment.

- Grade 4 neutropenia (ANC < 500 cells/mm³) lasting more than 7 consecutive days
- Grade 4 thrombocytopenia (platelet count < 25,000/ μ L) lasting more than 7 consecutive days
- Platelet count less than 10,000/ μ L at any time
- Grade 3 neutropenia with fever or infection, or both, where fever is defined as an oral temperature greater than 38.5°C
- Grade 3 thrombocytopenia with clinically significant bleeding

4.3.2 **Dose Modifications for Non-hematological Toxicities**

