If a patient experiences any of the following toxicities during the dosing period, dosing will be held for the remainder of that cycle and the dose will be decreased by 1 level (-10 mg) for all subsequent cycles of treatment, and treatment may resume after drug related toxicities have resolved to \leq Grade 1 or to baseline.

- Any Grade 3 non-hematological toxicity that is considered by the investigator to be related to study drug other than:
 - Grade 3 or greater nausea or emesis, or both, that occurs in the absence of optimal antiemetic therapy (5-hydroxytryptamine 3 [5-HT₃] serotonin receptor antagonist);
 - Grade 3 or greater diarrhea that occurs in the absence of optimal supportive therapy with loperamide or a comparable anti-diarrheal;
 - Grade 3 fatigue that lasts less than 1 week
- Grade 2 non-hematological toxicities that are considered by the investigator to be related to study drug and in the opinion of the investigator require dose reduction.
- Any grade 4 non-hematological toxicity that is considered by the investigator to be related to study drug. If, in the opinion of the investigator and the DMC, it is in the patient's interest to continue therapy with alisertib, the patient may resume therapy after recovery from a grade 4 to \leq Grade 1 or to baseline values; the dose of alisertib should be reduced by at least 1 dose level for subsequent cycles of therapy.

When intra-patient dose reduction of alisertib is required, no re-escalation of dose will be permitted. If a patient requires more than 2 dose reductions, therapy with alisertib will be discontinued.

4.4 **Management of Clinical Events**

4.4.1 **Nausea and vomiting**

Prophylactic antiemetic therapy will not be used in this study unless it becomes clear that alisertib causes acute nausea and vomiting. Although this study will not initially employ prophylactic antiemetics, there is no prohibition against antiemetic use in the management of a patient who develops nausea or vomiting, or both. If

prophylactic antiemetic therapy is needed, 5 HT3 receptor antagonists (without corticosteroids) should be tried first. Because of the potential of benzodiazepines to cause sedation, the use of benzodiazepines for antiemetic prophylaxis should be reserved for patients who cannot be satisfactorily managed otherwise.

4.4.2 **Diarrhea**

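### The hematologic stop-and-reduce rules in Section 4.3.1 name Grade 3 without a Grade 4 counterpart, so a deeper cytopenia with fever, infection or bleeding can escape the mandatory dose reduction that the milder one triggers

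*Combined protocol and SAP*

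**What the plan says.** Section 4.3.1 applies to "any of the following hematological toxicities during the dosing period". If one occurs, the rest of that cycle's doses are dropped and every later cycle is given one level (10 mg) lower. There are five triggers:

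1. Grade 4 neutropenia (ANC below 500) persisting beyond 7 days in a row.
2. Grade 4 thrombocytopenia (platelets below 25,000) persisting beyond 7 days in a row.
3. Platelets below 10,000 at any time.
4. "Grade 3 neutropenia with fever or infection, or both, where fever is defined as an oral temperature" above 38.5°C.
5. "Grade 3 thrombocytopenia with clinically significant bleeding".

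Section 4.3.2, for non-hematological toxicity, uses two styles. Its main rule is "Any Grade 3 non-hematological toxicity that is considered by the investigator to be related to study drug", with a separate bullet for Grade 4. Its exceptions are worded as a floor, for example "Grade 3 or greater diarrhea that occurs in the absence of optimal supportive therapy".

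Section 4.2 defines the schedule: "one cycle is defined as 21 days (days 8-21 will be rest days". Its restart rule begins "From Cycle 1-6, in order for each new cycle of therapy to begin, MF patients must meet the following criteria", namely ANC at least 1000 and platelets at least 50,000. It adds that "all toxicities considered to be related to therapy with alisertib must have resolved to" Grade 1 or baseline. The count limits do not apply to AMKL cytopenias judged to be due to the disease.

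**The concern.** Triggers 4 and 5 concern a low count with a complication, and they name Grade 3 alone. Triggers 1 and 2 concern Grade 4 but add a duration condition and make no mention of complications. A short Grade 4 episode with fever, infection or bleeding can therefore fall between them, while the milder count with the same complication is caught. That reverses the order of severity a dose rule should follow.

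At stake are patient safety and uniform dosing at three sites. Section 1.6 says that disturbed hematopoiesis puts both populations at increased risk of toxicity, and safety is the primary objective. Section 8.1.10 lists febrile neutropenia among events seen in at least 10% of patients in earlier trials. The planned adverse event tables are not distorted, because the events are recorded whichever way the rule is read.

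**Working it through.** **Inputs.** Grade 4 limits of ANC 500 and platelets 25,000, the 10,000 platelet trigger and the 7-day condition come from Section 4.3.1. Doses of 50 mg and 40 mg BID on Days 1-7 come from Sections 4.2 and 4.3. The maximum of 24 patients comes from Section 10.2. The Grade 3 upper limits (ANC 1000, platelets 50,000) are an assumption; they do not affect the gap, whose edges are all set by Section 4.3.1.

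**Step 1. Apply the five triggers literally, then with *or greater* added to triggers 4 and 5.**

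| Case | Literal text | With *or greater* |
|---|---|---|
| ANC 700, fever, 3 days | 4 | 4 |
| ANC 499, fever, 3 days | none | 4 |
| ANC 100, fever or infection, 7 days | none | 4 |
| ANC 100, fever, 8 days | 1 | 1, 4 |
| Platelets 30,000, bleeding, 3 days | 5 | 5 |
| Platelets 24,999, bleeding, 3 days | none | 5 |
| Platelets 10,000, bleeding, 7 days | none | 5 |
| Platelets 9,999, bleeding, 1 day | 3 | 3, 5 |
| Platelets 15,000, bleeding, 8 days | 2 | 2, 5 |

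The uncovered bands are ANC below 500 with fever or infection for 7 days or less, and platelets from 10,000 to below 25,000 with bleeding for 7 days or less.

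**Step 2. See whether another rule covers them.**

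- Section 4.3.2 acts only on non-hematological toxicity judged related to the drug. A related Grade 3-4 infection or bleed would be caught. Febrile neutropenia alone need not be, since Section 8.1.10 classes it as hematological.
- The restart criteria can delay a cycle but do not lower the dose. They are stated for Cycles 1-6 only.
- The delay rule in Section 4.3 lowers the dose only when recovery takes the delay past 1 week.
- The general provision in Section 4.3 for reducing or interrupting treatment is permissive.

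**Step 3. Work one example.** An MF patient on Cycle 2 Day 5 has ANC 300 and 39°C, no separate related Grade 3-4 event, and recovers by Day 11. No mandatory reduction applies, and Cycle 3 may start on time at 50 mg BID. With ANC 600 and the same fever, dosing stops and Cycle 3 is given at 40 mg BID.

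**Step 4. Size per affected patient.**

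- Next cycle, unreduced: 7 × 2 × 50 = 700 mg. Reduced: 7 × 2 × 40 = 560 mg. Ratio: 700/560 = 1.25.
- Current cycle, if found on Day 4 before dosing: Days 4-7 hold 4 × 2 = 8 of 14 doses (57%), or 8 × 50 = 400 of 700 mg, with no mandatory hematologic stop.

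**Step 5. The duration triggers.** If the dosing period means Days 1-7, a Grade 4 count beginning on Day 1 or later first exceeds 7 days on Day 8, a rest day. Triggers 1 and 2 then cannot stop that cycle's doses. Among Grade 4 counts, only platelets below 10,000 can.

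**Step 6. Number of patients.** The documents give no rate for these bands. At assumed rates of 1%, 2% and 5%: 24 × 0.01 = 0.24, 24 × 0.02 = 0.48, 24 × 0.05 = 1.2.

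**The case against.** The best reply is that nobody could have meant to reduce at ANC 600 with fever but not at ANC 300, so sites will read Grade 3 as a floor. That probably was the intent. But Section 4.3.1 treats Grade 4 as its own category with its own condition, and Section 4.3.2 either writes *or greater* or gives Grade 4 a separate bullet. A literal reading is reasonable, and the text does not exclude it.

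A second reply is that much of the gap is covered elsewhere. Section 8.1.10 lists fever and infection also under general abnormalities, so a related Grade 3-4 infection can trigger Section 4.3.2 by itself. Doses may be held at discretion, and serious events reach the quality assurance monitor within 24 hours and then the DMC. This stands in part: continued dosing through ANC 300 and 39°C is unlikely. What remains is neutropenic fever alone, and infection or bleeding that is lower-grade or judged unrelated. For these no reduction is mandatory unless the next cycle is delayed by more than 1 week.

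Third, the illustrations depend on chosen timing. Required blood counts in Cycles 2-6 fall on Days 1 and 15, so the Cycle 2 example needs an unscheduled count. The Day 4 count is scheduled only in Cycle 1, and the 57% figure is an illustration rather than an expected effect. That is fair.

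Fourth, a strict reading of the dosing period would leave complicated events starting after Day 7 without a trigger even after the change. That is true, but it is a separate ambiguity in the lead-in sentence and does not excuse the two bullets.

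**Conclusion.** The concern holds. As written, triggers 4 and 5 give a wrong result: the milder count with a complication must be reduced, while the deeper count with the same complication for 7 days or less need not be. The claim is limited to a mandatory hematologic trigger; discretion and Section 4.3.2 remain. Per affected patient at the starting dose, the difference is 140 mg in the next cycle (700 against 560 mg). Few patients are likely to be affected: 0.2 to 1.2 of 24 at assumed rates of 1% to 5%, which have no source in the documents. The omission itself is certain; how often it would change a patient's dose is not known. It should be corrected on grounds of safety and consistency between sites.

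**What to change.** In Section 4.3.1, change bullet 4 to cover Grade 3 *or greater* neutropenia with fever or infection, or both, *of any duration*, keeping the 38.5°C definition. Change bullet 5 to cover Grade 3 *or greater* thrombocytopenia with clinically significant bleeding, *of any duration*. Leave the other three bullets unchanged.

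The cost is a wording change to two bullets in an amendment and a memo to sites, with no new tests or patients. The downside is possibly a few more dose reductions, most likely in AMKL patients, who can enter with low counts because Section 3.1.4 sets no ANC or platelet minimum. If cytopenias due to the disease are to be exempt, as in Section 4.2, the same two bullets should say so. The amendment could also state whether the dosing period means Days 1-7 or the whole cycle.

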4.5 Concomitant Medications/Treatments

In general, the use of any concomitant medication/therapies deemed necessary for the care of the patient is permitted, except as specifically prohibited (see Sections 4.5.1 and 4.5.2 below),

4.5.1 Prohibited Concomitant Medications/Treatments

The following medications and procedures are prohibited during the study:

- Any antineoplastic therapy other than alisertib
- Alternative therapy, including palliative radiotherapy, for treatment of the patient's malignancy
- Any investigational therapy other than alisertib
- Requirement for administration of any proton pump inhibitor. Use of any PPI in either continued or intermittent use will be prohibited during the conduct of the study and patients must discontinue any use of PPI within five days prior to the first dose of alisertib. Patients may be administered alternative agents to manage gastric acidity or reflux (eg, H2 receptor antagonists, antacids) with exceptions described below:
 - Histamine-2 (H2) receptor antagonists are not permitted from the day prior (Day -1) through to the end of alisertib dosing (e.g., Day 7)
- Strong UGT 1A1/2/8 and CYP 3A4, 2C9, 2C19, and 1A2 enzyme inducers or inhibitors, such as the enzyme-inducing antiepileptic drugs phenytoin, carbamazepine or phenobarbital, or rifampin, rifabutin, rifapentine unless medically necessary (see Appendix III)
- Patients should be strongly encouraged to avoid herbal remedies, including:
 - St. John's wort (strong inducer of CYP3A4)
 - Grapefruit juice (strong inhibitor of CYP3A4)

4.5.2 Permitted Concomitant Medications/Treatments

- Myeloid growth factors to treat patients with neutropenia according to the ASCO guidelines.
- Antiemetic agents may be administered at the discretion of the investigator but are not commonly required as a prophylactic agent.
- Antacids are permitted; however, they should be administered more than 2 hours before or 2 hours after administration of alisertib.
- Medications with potential CNS effects are not prohibited in this study, but it is recommended that their use be minimized to avoid confusion in the interpretation of CNS effects should they occur during the course of treatment with alisertib. Because of alisertib's structural and pharmacological similarity to the benzodiazepines, concomitant therapy with benzodiazepines is discouraged but not prohibited.
- Patients actively receiving hydroxyurea are eligible and may continue to receive hydroxyurea through cycle 1 of protocol treatment.
(Note: If the platelet count remains above 1 million after cycle 1, hydroxyurea can be used at the treating physician's discretion, if the platelets are $1000 \times 10^9/L$, or more, or if there are symptoms from thrombocytosis).
- Medications that can potentially reduce or increase effectiveness of alisertib, UGT 1A1/2/8 and moderate CYP 3A4, 2C9, 2C19, and 1A2 enzyme inducers or inhibitors, should be used with caution (see appendix III).
- All other medical conditions should be treated at the discretion of the investigator in accordance with local community standards of medical care.

4.6 Duration of Therapy

Patients may continue to receive alisertib treatment until any of the following occur:

- Disease progression
- Development of an inter-current illness that prevents further administration of treatment
- Unacceptable adverse event(s)
- Patient decides to withdraw from either study treatment or the as a whole study
- The treating investigator determines that the patient should be taken off treatment for any reason (i.e. changes in condition, inability to comply with study treatment or procedures)

4.7 Duration of Follow Up

Once off treatment for any reason, patients will have an end-of-treatment visit at approximately 30 days after their last dose of alisertib. Patients who are experiencing on-going toxicities at this time will continue to be followed until resolution of the toxicity (either return to baseline or stabilization). In addition, there will be a final off-study visit approximately 6 months after the last dose of treatment to assess for late-onset toxicity.

4.8 Termination of Study Treatment and/or Study as a Whole

Patients can be taken off the study treatment and/or study as a whole at any time at their own request, or they may be withdrawn at the discretion of the investigator for safety, behavioral or administrative reasons. The reason(s) for discontinuation must be clearly documented on the appropriate eCRF and may include:

- Patient voluntarily withdraws from treatment (follow-up permitted)
- Patient withdraws consent (no follow-up permitted)
- Patient is unable to comply with protocol requirements
- Patient demonstrates disease progression
- Patient experiences unacceptable toxicity
- Patient experiences treatment delay of > 2 weeks due to toxicity
- Treating physician determines that continuation on the study would not be in the patient's best interest
- Patient becomes pregnant
- Patient develops a second malignancy that requires treatment which would interfere with this study
- Patient develops an intercurrent illness that interferes with study treatment.
- Patient becomes lost to follow-up (LTF)

5.0 STUDY PROCEDURES

5.1 Schedule of Events for MF Patients

	Baseline	On-Treatment ⁱ							Off-Treatment	
	Screening	Cycle 1 ^a				Cycles 2-6 ^q +/- 2 days		Cycle 7+ ^m +/- 2 days	EOT Visit ^o	EOS Visit ^p
		D1 ⁱ	D4 (+/- 1d)	D8 (+/-2 d)	D15 (+/-2 d)	D1 ⁱ	D15	D1		
Informed consent ^v	X									
Medical history ^r	X									
Physical exam ^b	X	X		X	X	X		X	X	X
ECOG status ^s	X	X		X	X	X		X	X	X
Vital signs ^c	X	X		X	X	X		X	X	X
12-lead ECG ^d	X									
Hematology ^{e,t}	X	X	X	X	X	X	X	X	X	X
Chemistry ^{f,t}	X	X	X	X	X	X	X	X	X	X
DIC screen ^{g,t}	X									
PT(INR)/aPTT ^g		X	X	X	X	X				
Pregnancy test ^{h,t}	X	X								
Palpation for splenomegaly ^l	X	X				X		X		
MPN-SAF ^l	X	X				X		X		
Bone marrow biopsy & aspirate ^k	X							X ^k	X	
Bone marrow collection for PD studies ^{i,j}					X					
Blood collection for PD studies ^{i,j}		X			X	X	X			
Treatment ⁿ					X					
Adverse events ^u	X	X		X	X	X		X	X	X
Concomitant meds	X	X		X	X	X		X	X	

^a One cycle = 21 days.

^b Includes height (baseline only) and weight. Baseline physical exam within 14 days of registration.

^c Vital signs include diastolic and systolic blood pressure, heart rate, and oral temperature; C1D1 vital signs should be taken pre-dose(+/-30 mins) as well as about 2 hours(+/-30mins) post dose.

^d A 12-lead ECG will be performed at baseline and thereafter only as clinically indicated. Baseline ECG within 14 days of registration

- ^e Hematology panel to include hematocrit, hemoglobin, white blood cell count with differential, and platelet count. Samples should be collected days 1, 4, 8, and 15 of cycle 1, days 1 and 15 of cycles 2-6, and then day 1 of all cycles thereafter (a window of +/- 2 days is permitted for all timepoints). See footnote t.
- ^f Chemistry panel to include the following: BUN, creatinine, sodium, potassium, chloride, bicarbonate, glucose, uric acid, LDH, total bilirubin, direct bilirubin, ALP, AST (SGOT), ALT (SGPT), albumin, magnesium, phosphate, and calcium. Samples should be collected days 1, 4, 8, and 15 of cycle 1, days 1 and 15 of cycles 2-6, and then day 1 of all cycles thereafter (a window of +/- 2 days is permitted for all timepoints). See footnote t. Beyond Cycle 6, magnesium and phosphate testing is not required (as part of the chemistry panel).
- ^g Disseminated intravascular coagulation (DIC) screen should include: PT/INR, aPTT, fibrinogen, and D-dimer. Cycle 1 day 1 PT/INR/aPTT does not need to be performed if the screening DIC was within 3 days of this visit. If the initial DIC is positive follow-up coagulation studies should include the full DIC panel (rather than the PT/INR/aPTT alone). See footnote t.
Note: Beyond Cycle 6, PT/INR, aPTT testing is not required.
- ^h Serum pregnancy test required for women of child-bearing potential during screening AND pre-dose on Cycle 1 day 1. Results must be available and negative prior to dosing. See footnote t.
- ⁱ It is strongly preferred that correlative samples be collected and shipped only on Monday – Thursday (with same day shipment preferred). Friday collections/shipments should be avoided to ensure sample stability. Since these samples are collected on Day 1 of each cycle, it is preferred that Day 1 visits be conducted on Monday through Thursday when correlative samples are being collected. Sites should use the available windows to achieve this. Please contact the QAM if there are any questions
- ^j Peripheral blood (25 ml) and/or bone marrow (bone marrow only if done clinically – will collect about 10-20 ml) samples will be collected for determination of alisertib pharmacodynamics (PD studies). Blood samples will be collected at the start of each cycle (D1). Sample collection at D15 will be optional. (Samples will be collected for a maximum of 6 cycles). Correlative bone marrow samples should be obtained any time bone marrows are collected as clinically indicated during study participation. . At baseline, correlative bone marrow collection is not mandatory for study entry. However, study team should request 3-4 unstained slides from any prior bone marrow testing performed within the last year before study entry. Please refer to laboratory manual for details.
- ^k Bone marrow aspirate and biopsy is required within 1 year prior to registration (provided the PI confirms the diagnosis and there is no suspicion for acceleration to blast phase), on C7D1 (+/-14 days) and thereafter only as clinically indicated.
- ^l Palpation for splenomegaly and MPN-SAF will be done only on MF patients. Baseline MPN-SAF and palpation for Splenomegaly within 14 days of registration
- ^m Beyond Cycle 6, if the patient's condition is stable, then they will be required to come in only on Day 1 of every even cycle (every 6 weeks) for study visit. In that case, for those visits when patient is not coming to clinic for study visit, CBC and CMP only will be done in an outside laboratory convenient for the patient, and results will have to be faxed to the clinic. Patients can start their treatment at home only after the treating physician has reviewed the laboratory results and determined that they are able to continue treatment. For these cycles, the study coordinator will contact the patient on/prior to Day 1 to inform them if they can or cannot start the new cycle, and also check compliance regarding study drug intake.
- ⁿ Patients will be administered orally on days 1-7 of each cycle (1 cycle = 21 days); patients may remain on treatment until development of unacceptable toxicity or progression of disease.
- ^o Patients will have an end of treatment (EOT) visit approximately 30 days (+10 days) after the last dose of treatment; if a bone marrow was carried out at disease progression, this will be considered the EOT marrow and does not need to be repeated at the EOT visit.
- ^p Patients will have a final end of study (EOS) visit approximately 6 months (+/- 30 days) after the last dose of treatment to assess for late-onset toxicity.

^q Labs required only on days 1 and 15 of cycles 2-6, but in the event of cycle 1 toxicity or at treating investigator's discretion, additional interim labs may be performed per standard of care.

^r Baseline Medical History within 14 days of registration

^s Baseline ECOG Status within 14 days of registration.

^t Baseline Hematology, Chemistry, DIC screen, Pregnancy Test, within 14 days of registration

^u Baseline Adverse Events and Concomitant Medications within 14 days of registration.

^v Informed consent should be obtained within 28 days of registration.

